## 8.6.2 Anti-N8-GP antibodies

N8-GP binding antibodies will be assessed using a radioimmunoassay that is validated according to internationally recognised guidelines. Samples measured above the assay cut-point of antibody reactivity will be subject to a confirmation test, where the presence of anti-N8-GP antibodies will be confirmed by addition of excess of unlabelled N8-GP and cross-reactivity to rFVIII will be measured using excess of unlabelled rFVIII. Only samples positive in the confirmatory assay will

be characterised as anti-N8-GP or anti-rFVIII antibody positive. The analyses will take place at the end of the trial.

### 8.6.3 Anti-PEG antibodies

Anti-PEG antibodies will be measured at baseline and at end of treatment using a direct ELISA validated according to internationally recognised guidelines. Samples measured above the assay cut-point of antibody reactivity will be subject to a confirmation test, where the presence of anti-PEG antibodies will be confirmed by addition of excess of unlabelled PEG. The analysis will take place at the end of the trial.

### 8.6.4 Anti-HCP antibodies

All patients at baseline and subsequently any patient who experiences an acute severe allergic/anaphylactic reaction (see Section 10.3.3 for definition) that cannot be assigned to anti-N8-GP antibodies will be assessed for anti-HCP antibodies. The blood sample for assessment of anti-HCP antibodies should be drawn within 4 weeks (and preferably 2-4 weeks) after the AE of acute severe allergic/anaphylactic reaction.

## 8.7 Diary

The patient/caregiver will be provided with a diary for recording of bleeding episodes and the home treatment hereof. All the treatments, administered at home (see section 8.8 and 8.1.1) must also be recorded in the diary. All bleeding episodes including the bleeding episodes that are experienced while at site must be recorded in the diary. At visit 1, the patient/caregiver will receive the first diary and they will be trained in the use by the investigator.

The diary is split into a bleed and a treatment diary. The diaries must be returned at every scheduled visit and new diaries will be handed out to the patient/caregiver. During trial site visits, the diaries must be reviewed together with the patient/caregiver and evaluate together with the patient/caregiver the correctness of the haemostatic efficacy for treatment of bleeds. The severity rating of the bleeding episode and the treatment type must be entered by the trial site staff, if necessary, into the diaries. Afterwards the diary data must be recorded in the eCRF by the investigator or the designee.

Patient diaries must be reviewed by the investigator at every scheduled visit to ensure that AEs, including any change in health and concomitant medication, are reported. Furthermore, the diaries must also be reviewed for accuracy, completeness and consistency with the requirements defined in this protocol, see section 6.4. This review must be documented in the patient's medical record.

Only the patient or caregiver is allowed to change entries in the diary except for the severity rating and treatment type if they are entered into the diary by the site.

If clarification of entries or discrepancies in the diary that are entered by the patient is needed, the patient must be questioned, and a conclusion made in the patient's medical record. Care must be taken not to bias the patient. A correction is done by both changing the entry in the paper diary and the entry in the eCRF.

## 8.8 Home treatment training

Home treatment training with injection of N8-GP (turoctocog alfa pegol) can start after injections of the first dose at the trial site, and should continue until the patient or caregiver is comfortable with the reconstitution and injection process. The training must be documented in the medical records.

A home treatment guide for the reconstitution and injection process must be handed-out to the patient or caregiver at every dispensing visit.

If the patient does not follow the planned dosing schedule, the investigator must retrain the patient and/or caregiver.

# 9 Statistical considerations

## 9.1 Statistical hypotheses

No confirmatory hypotheses are planned to be tested due to the low number of patients to be included in this trial.

## 9.2 Sample size determination

No formal sample size calculations have been performed. Based on meeting communication with CDE and with the supplement data from the global pivotal trial NN7088-3859 which also included Asian patients, a total number of 30 Chinese patients to complete this trial is considered sufficient to evaluate efficacy and safety in the Chinese population.

Fifteen (15) patients will participate in PK assessments sessions to ensure at least 12 patients with complete single-dose and steady-state PK profiles.

## 9.3 Populations for analyses

All patients exposed to N8-GP in this trial will be included in the full analysis set and the safety analysis set.

Exceptional outlier pharmacokinetic profiles and/or individual plasma FVIII activities may be excluded when analysing pharmacokinetic endpoints based on the FAS. The rules to exclude data points from analysis of pharmacokinetic endpoints are described in the statistical analysis plan (SAP), and the decision of data exclusion will be made during a review prior to database lock. Any excluded data points will be documented in the database lock minutes and also in the clinical trial report (CTR).

## 9.4 Statistical analyses

The statistical analysis plan (SAP) will be finalised prior to first-patient-first visit (FPFV), and it will include a more technical and detailed description of the statistical analyses described in this section. This section is a summary of the planned statistical analyses of the most important endpoints including primary endpoint. There are no confirmatory secondary endpoints specified in this trial.

### 9.4.1 General considerations

Novo Nordisk will be responsible for the statistical analyses.

Summaries for continuous endpoints will include total number (N), mean (SD), median and min/max, and for pharmacokinetic endpoints also geometric mean and coefficient of variation (CV%). Summaries for categorical endpoints will include N, number (n) and percentages (%) for each outcome category.

In general, all summaries and analyses will also be prepared by age subgroup (12-17 and 18-70 years of age).

### 9.4.2 Primary endpoint

Endpoint title	Time frame	Unit
Number of bleeding episodes	From start of treatment until visit 7	Count

The primary endpoint will be analysed by a Poisson regression model allowing for over-dispersion (using Pearson's chi-square divided by the degrees of freedom) with the logarithm of duration of actual prophylaxis treatment with N8-GP used as offset. Estimates of the annualised bleeding rate (ABR) will be provided with 95% confidence intervals.

Only the observed bleeding episodes will be counted and the offset will be the duration of actual prophylaxis treatment with N8-GP.

A sensitivity analysis based on negative binomial regression model with the logarithm of duration of actual prophylaxis treatment with N8-GP used as offset will also be performed.

Another sensitivity analysis will be performed imputing the number of bleeding episodes for patients that discontinue treatment. For patients prematurely discontinuing treatment, the number of bleeding episodes counting in the analysis will be imputed up to what they could be expected to have had if they had completed the trial on treatment. If e.g. a patient withdraws after 2 months with 3 bleeding episodes, but the patient should have been in the study for 6 months, then this patient will in the analysis count as having had 9 bleeding episodes in 6 months. This is similar to last observation carried forward (LOCF) and will avoid positive bias occurring from patients with many bleeding episodes withdrawing early. For patients withdrawing within 1 month this method is

Protocol  
Trial ID: NN7088-4595~~CONFIDENTIAL~~Date:  
Version:  
Status:  
Page:05 July 2021  
4.0  
Final  
60 of 102***Novo Nordisk***

considered to give too uncertain LOCF values, hence imputation will not be attempted for such patients. Instead only the observed bleeds and the observed duration will be used.

ABRs will be summarised in total, by cause of bleed, and by location of bleed (including ABR in baseline target joints).

Bleeding episodes in relation to surgery will not be included in the analysis.

## 9.4.3 Secondary endpoints

### 9.4.3.1 Secondary efficacy endpoints

Endpoint title	Time frame	Unit
Haemostatic effect of N8-GP when used for treatment of bleeding episodes, assessed on a four-point scale for haemostatic response (excellent, good, moderate and none) by counting excellent and good as success and moderate and none as failure.	From start of treatment until visit 7	Count
Consumption of N8-GP for treatment of bleeding episodes	From start of treatment until visit 7	IU/kg/bleed
Consumption of N8-GP for prophylaxis	From start of treatment until visit 7	IU/kg/year
FVIII trough activity during prophylaxis	From start of treatment (excluding the first exposure) until visit 7	IU/mL

#### Haemostatic effect of N8-GP

Haemostatic effect of N8-GP when used for treatment of bleeding episodes is assessed as success/failure based on a four-point scale for haemostatic response (excellent, good, moderate and none). Excellent and good counts as success and moderate and none as failures. In addition, any bleeding episodes with missing response information will be counted as failures.

Specifically, this will be done by a logistic regression. The analysis will be performed by use of Proc Genmod in SAS. Correlation within patients will be taken into account using a Generalized Estimation Equations approach with a working correlation matrix with a compound symmetry structure.

Response as measured by the four point scale will also be summarised and listed.

A sensitivity analysis will be performed similar to the primary analysis but only analysing bleeding episodes with recorded responses (i.e. not counting any bleeding episodes with missing response as failures).

The haemostatic effect will be summarised in total, by cause of bleed and by location of bleed (including haemostatic effect in target joints).

Haemostatic effect for bleeding episodes in relation to surgery will not be included in the analysis.

**Consumption of N8-GP for treatment of bleeding episodes**

The number of injections per bleed will be summarised and listed.

The number of IU/Kg per bleed will be summarised and listed.

**Consumption of N8-GP for prophylaxis**

The number of injections for prophylaxis will be summarised and listed.

The number of IU/Kg per month and per year will be summarised and listed.

**FVIII trough activity during prophylaxis**

The trough and recovery FVIII activity levels will be analysed by a mixed model on the log-transformed plasma FVIII activity with age group as fixed effect and patient as a random effect. The mean trough and recovery levels will be presented back-transformed to the natural scale together with the 95% confidence interval.

The following rules will be implemented for the analysis of trough and recovery levels:

- Pre-dose and post-dose values will be excluded if post-dose activity is  $\leq$  pre-dose activity.
- Pre-dose and post-dose values taken more than  $\pm 2$  days outside of dosing interval will be excluded.
- Pre-dose and post-dose values taken less than twice the prophylaxis treatment interval after last treatment of a bleeding episode will be excluded.
- Pre-dose and post-dose values taken within 2 weeks after surgery will be excluded.
- Pre-dose and post-dose values taken in relation to the first exposure will be excluded.
- FVIII activity measured in defrosted plasma samples will be excluded.

Furthermore, trough and recovery (30 minutes post-dose) levels measured at scheduled visits will be summarised and listed. Incremental recoveries will be calculated and presented in summary tables and plots.

### 9.4.3.2 Secondary safety endpoints

Endpoint title	Time frame	Unit
Incidence rate of confirmed FVIII inhibitors $\geq 0.6$ BU	From start of treatment until visit 7	Rate
Number of adverse events (AEs)	From start of treatment until end of trial	Count
Number of serious adverse events (SAEs)	From start of treatment until end of trial	Count

#### Incidence Rate of Confirmed FVIII-inhibitors $\geq 0.6$ BU

A patient is said to have FVIII-inhibitors if two consecutive tests, preferably within 2 weeks, are positive ( $\geq 0.6$  BU). The rate of inhibitors will be reported and a 1-sided 97.5% upper confidence limit will be provided based on an exact calculation for a binomial distribution. For the calculation of the inhibitor rate the nominator will include all patients with neutralising antibodies while the denominator will include all patients with a minimum of 50 exposures plus any patients with less than 50 exposures but with neutralising inhibitors.

#### Adverse Events (AEs) and Serious Adverse Events (SAEs) reported during the trial

Treatment emergent AEs (TEAEs defined as AEs occurring after dosing with trial product) and treatment emergent SAEs (TESAEs) will be summarised by frequency of events and frequency of patients with any event. Similar summaries cross-classified by severity and by causal relation to trial product will be made.

Furthermore, listings will be provided displaying all TEAEs and TESAEs including pertinent clinical information.

### 9.4.3.3 Secondary pharmacokinetic endpoints

**Table 9-1 Definition and calculation of PK Parameters**

Title	Time frame	Unit	Details
Incremental Recovery	30 min $\pm$ 5 min post-injection at visit 2a and visit 7	(IU/mL)/(IU/kg)	The incremental recovery is calculated by subtracting the FVIII activity (IU/mL) measured in plasma at time 0 from that measured at time 30 min after dosing and dividing this difference by the dose injected at time 0 expressed as IU/kg BW
FVIII activity 30 min post-injection ( $C_{30\text{min}}$ )	30 min $\pm$ 5 min post-injection at visit 2a and visit 7	IU/mL	The FVIII activity recorded 30 min after end of injection. Expected to be the maximum FVIII activity observed.
FVIII trough activity 96 h post-injection ( $C_{96\text{h}}$ )	96 h $\pm$ 8 h post-injection at visit 2a and visit 7	IU/mL	The FVIII activity recorded immediately before next dose is given. Expected to be the minimum FVIII activity observed.
AUC (0-inf)	0–96 h post-injection at visit 2a and visit 7	h*(IU/mL)	Area under the activity versus time profile from time zero to infinity. Measure of total plasma exposure. $AUC_{(0-\text{inf})} = AUC_{(0-t)} + C_{(t)} / \lambda_z$ , where $C_{(t)}$ is the last measurable activity.
AUC (0-t)	0–96 h post-injection at visit 2a and visit 7	h*(IU/mL)	Area under the plasma activity versus time profile from time zero to the last measurable activity. Measure of plasma exposure in the time interval 0 to last measurable activity. $AUC_{(0-t)}$ is calculated using the linear trapezoidal method from time 0 to the time for the last measurable activity. The activity at time 0 will be estimated by log-linear back extrapolation of the two initial post-administration activities. If the second value is not lower than the first value, the concentration at time 0 will be defined as the highest of these two.
AUC (0-96h)	0–96 h post-injection at visit 2a and visit 7	h*(IU/mL)	AUC (0-96h) is calculated using the linear trapezoidal activities. If FVIII activities are not available up to 96 hours post-dose, the area under the missing terminal part of the curve will be

Title	Time frame	Unit	Details
			determined by interpolation or extrapolation using a similar principle as for $AUC_{(0-\infty)}$ , where the terminal elimination rate constant, $\lambda_Z$ , is used given that there are sufficient measurements for the determination of the terminal elimination rate constant.
Accumulation ratio	0–96 h post-injection at visit 7		Accumulation ratio is calculated as $AUC_{(0-96h)}$ at steady state/ $AUC_{(0-96h)}$ at single dose.
Terminal half-life ( $t_{1/2}$ )	0–96 h post-injection at visit 2a and visit 7	h	$t_{1/2} = \ln(2) / \lambda_Z$ , where $\lambda_Z$ is the terminal elimination rate. The terminal elimination rate will be estimated using linear regression on the terminal part of the log(activity) versus time profile.
Clearance (CL)	0–96 h post-injection at visit 2a and visit 7	mL/h/kg	CL = Dose / AUC. Using $AUC_{(0-\infty)}$ for single dose and $AUC_{(0-96h)}$ for steady state.
$V_Z$	0–96 h post-injection at visit 2a and visit 7	mL/kg	Apparent volume of distribution based on the terminal phase. $V_Z = CL/\lambda_Z$
$V_{ss}$	0–96 h post-injection at visit 7	mL/kg	Apparent volume of distribution at steady-state. $V_{ss} = CL \cdot MRT$
%extrap	0–96 h post-injection at visit 2a and visit 7	%	Percentage of $AUC_{(0-\infty)}$ determined by extrapolation. $AUC_{(t-\infty)}/(AUC_{(0-\infty)})$
MRT	0–96 h post-injection at visit 2a and visit 7	h	Mean Residence Time. MRT = $AUMC/AUC_{(0-\infty)}$ , where AUMC is the area under the first moment curve, i.e. the area under the curve $t \cdot C_{(t)}$ , calculated with the same method as $AUC_{(0-\infty)}$ (linear trapezoidal method + extrapolated area)
$\lambda_Z$	0–96 h post-injection at visit 2a and visit 7	1/h	Terminal elimination rate constant. The terminal elimination rate constant will be estimated using linear regression on the terminal part of the log(activity) versus time profile

Single dose PK will be based on the PK session at visit 2a, and steady state PK will be based on the PK session at visit 7.

Protocol  
Trial ID: NN7088-4595~~CONFIDENTIAL~~Date:  
Version:  
Status:  
Page:05 July 2021  
4.0  
Final  
66 of 102**Novo Nordisk**

The PK parameters will be calculated using plasma FVIII activity obtained from the chromogenic assay. The PK parameters will be derived according to a non-compartmental method, as described in [Table 9-1](#). The actual time points will be used in the calculations.

If any profiles and/or individual plasma FVIII activities are excluded from the primary pharmacokinetic analysis, a sensitivity pharmacokinetic analysis will also be performed and reported based on all observed data. The primary pharmacokinetic analysis is based on the full analysis set excluding outliers.

Specifically, which data points and profiles that will be excluded will be defined prior to database lock. It should exclude profiles with pre-dosing activity > 5% (possibly indicating inadequate wash out) at visit 2a and profiles that are not indicative of a normal intravenously injection (i.e. clearly increasing plasma FVIII activity initially). If a patient is treated with an additional dose during the PK session, the plasma FVIII activities after the occurrence will then be excluded. Furthermore, if the profile shows indications of an additional dose (e.g. clearly increased plasma FVIII activity), the plasma FVIII activities after the occurrence will then also be excluded.

All pharmacokinetic endpoints (except MRT, Vss, Vz, percentage of  $AUC_{(0-\infty)}$  determined by extrapolation and terminal elimination rate constant) will be analysed using mixed effects model on log-transformed parameters including patient as random effect. Estimates of each endpoint with 95% confidence intervals will be provided back-transformed to the natural scale.

Individual and mean PK profiles will be presented graphically.

Furthermore, the mean PK endpoints will be summarised and individual PK endpoints will be listed.

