addition, prophylactic treatment can be time consuming. While prophylaxis is the standard of care for haemophilia, patients often face challenges integrating prophylaxis dosing into their daily life. Thus, therapies that require less frequent dosing may reduce the overall burden of prophylaxis. Currently, there are no extended half-life rFVIII products available in China, therefore Chinese patients will still be facing the above-mentioned barriers.

With the well-established knowledge of N8-GP efficacy and PK properties obtained from the comprehensive global clinical development program in severe haemophilia A patients across all age groups, N8-GP provides a new treatment option to significantly reduce the dosing frequency associated with regular prophylaxis, which fulfils the urgent unmet needs in Chinese patients.

Turoctocog alfa pegol (in this protocol referred to as 'N8-GP'), a 40-kDa glycoPEGylated human recombinant coagulation factor VIII (rFVIII) with an extended half-life, has been developed to offer patients with haemophilia A a more effective and less burdensome treatment versus standard FVIII products. N8-GP has improved PK properties including a 1.6-fold increase in terminal half-life compared with standard FVIII products, which offers the possibility of achieving FVIII levels in the range of moderate haemophilia A with a less-burdensome every fourth day treatment regimen. With a better overall PK profile and the ability to sustain higher FVIII levels than standard therapies, N8-GP has the potential to improve prophylaxis and simplify management of bleeds as well as perioperative haemostatic control in patients with haemophilia A.

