Major and minor surgery is allowed in the trial, and the haemostatic effect and consumption of N8-GP in relation to surgery will be evaluated.

Fifteen (15) of the 36 enrolled patients will participate in PK assessments to obtain at least 12 patients with two PK profiles of N8-GP (one single-dose PK profile and one steady-state PK profile). The single-dose PK assessments will be performed at first exposure to N8-GP after a preceding wash-out period of at least 4 days (96 hours). The steady-state PK assessments will be performed approximately 28 weeks after start of prophylaxis.

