## 8.5 Pharmacokinetics

Patients will be administered a single i.v. bolus injection of 50 IU/kg of N8-GP at Visit 2a and at Visit 7. The PK sessions extends over 96 hours. Overnight stay is not required. After completion of the PK sessions the patients will return to prophylaxis treatment with the next visit in line.

Patients must not have received current FVIII product for at least 4 days (96 hours) prior to the administration of trial product for the single-dose PK session at visit 2a, (i.e., a wash-out period of at least 96 hours must be applied before visit 2a).

There is no wash-out period for the steady-state PK session at visit 7, however administration of trial product at visit 7 should be approximately 96 hours after the previous N8-GP dose.

Patients must not be actively bleeding during the pharmacokinetic sessions.

The lines/tubes must be flushed immediately after administration of the trial product.

The pharmacokinetic endpoints (see Section [3.2.2.3](#)) will be based on assessments performed from 1 hour prior to and up to 96 hours after administration of N8-GP at Visit 2a (single-dose PK assessments) and Visit 7 (steady-state PK assessments) (see flowchart for PK assessments in Section [1.2](#)).

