**Novo Nordisk**

Title	Time frame	Unit	Details
AUC (0-t)	0–96 h post-injection at visit 2a and visit 7	h*(IU/mL)	
Area under the plasma activity versus time profile from time zero to the last measurable activity. Measure of plasma exposure in the time interval 0 to last measurable activity.
 
AUC(0-t) is calculated using the linear trapezoidal method from time 0 to the time for the last measurable activity. The activity at time 0 will be estimated by log-linear back extrapolation of the two initial post-administration activities. If the second value is not lower than the first value, the concentration at time 0 will be defined as the highest of these two.

AUC (0-96h)	0–96 h post-injection at visit 2a and visit 7	h*(IU/mL)	
AUC(0-96h) is calculated using the linear trapezoidal activities. If FVIII activities are not available up to 96 hours post-dose, the area under the missing terminal part of the curve will be determined by interpolation or extrapolation using a similar principle as for AUC(0-inf), where the terminal elimination rate constant, <math>\lambda_Z</math>, is used given that there are sufficient measurements for the determination of the terminal elimination rate constant.

Accumulation ratio	0–96 h post-injection at visit 7		
Accumulation ratio is calculated as AUC(0-96h) at steady state/AUC(0-96h) at single dose.

Terminal half-life (t 1/2 )	0–96 h post-injection at visit 2a and visit 7	h	
<math>t_{1/2} = \ln(2) / \lambda_Z</math>, where <math>\lambda_Z</math> is the terminal elimination rate. The terminal elimination rate will be estimated using linear regression on the terminal part of the log(activity) versus time profile.

Clearance (CL)	0–96 h post-injection at visit 2a and visit 7	mL/h/kg	
CL= Dose / AUC.    Using AUC(0-inf) for single dose and AUC(0-96h) for steady state.

Vz	0–96 h post-injection at visit 2a and visit 7	mL/kg	
Apparent volume of distribution based on the terminal phase.  <math>Vz = CL / \lambda_Z</math>

Vss	0–96 h post-injection at visit 7	mL/kg	
Apparent volume of distribution at steady-state.  <math>Vss = CL * MRT</math>

%extrap	0–96 h post-injection at visit 2a and visit 7	%	
Percentage of AUC(0-inf) determined by extrapolation.  <math>AUC_{(t-inf)} / (AUC_{(0-inf)})</math>

Statistical Analysis Plan  
 Trial ID: NN7088-4595  

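### The accumulation ratio has no term for the IU/kg recorded as injected, so a dose difference of a few per cent between the two PK sessions, if one occurs, could create or mask the small accumulation it measures

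*Protocol*

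**What the plan says.** Protocol section 9.4.3.3, Table 9-1, gives the ratio as follows: "Accumulation ratio is calculated as $AUC_{(0-96h)}$ at steady state/ $AUC_{(0-96h)}$ at single dose". SAP section 5.4.3, Table 2, has the same definition: "Accumulation ratio is calculated as AUC (0-96h) at steady state/AUC (0-96h) at single dose". Neither contains a dose.

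Elsewhere the same tables do use the dose. Incremental recovery is obtained by "dividing this difference by the dose injected at time 0 expressed as IU/kg BW", and clearance is dose over AUC, with AUC(0-inf) for the single dose and AUC(0-96h) at steady state.

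On the doses themselves, Protocol section 8.5 states: "Patients will be administered a single i.v. bolus injection of 50 IU/kg of N8-GP at Visit 2a and at Visit 7". On timing, Protocol section 4.1 says: "The steady-state PK assessments will be performed approximately 28 weeks after start of prophylaxis". Section 8.5 adds that "administration of trial product at visit 7 should be approximately 96 hours after the previous N8-GP dose".

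The secondary PK endpoints in Protocol section 3.2.2.3 include AUC, C30min, C96h, incremental recovery, half-life and clearance. The accumulation ratio is not among them. It is also not among the parameters that section 9.4.3.3 exempts from the mixed model, so on a literal reading it would be reported with an estimate and a 95% confidence interval.

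**The concern.** The ratio is the one parameter in the tables that directly sets one session against the other, and it leaves out a quantity that can differ between them. If the IU/kg injected at visit 7 is not the same as at visit 2a, the difference goes almost fully into the ratio and looks like accumulation, or like its absence.

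This matters because the quantity being measured is itself only a few per cent at a 96 h interval. The PK exclusion rules in section 9.4.3.3 cover pre-dose activity above 5% at visit 2a, abnormal initial profiles and additional doses. They set no tolerance on the size of the PK dose. Under Protocol section 10.3.3 a dose deviation counts as a medication error only if clinical consequences were likely, so a difference of a few per cent would not be flagged that way. At stake is the reading of a supportive PK parameter based on 12 to 15 pairs of profiles. The primary endpoint is not touched.

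**Working it through.** The documents state no expected accumulation ratio, no half-life in hours and no dose tolerance, so there is no planned figure to reproduce. The check asks how large the ratio should be, and what dose difference would match the accumulation.

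**Inputs**
- Dosing interval 96 h and nominal dose 50 IU/kg at both sessions (Protocol 8.5).
- Half-life: Protocol 2.2 gives only a comparison, "including a 1.6-fold increase in terminal half-life compared with standard FVIII products". A range of 12 to 24 h is assumed.
- Rise of about 2% per unit (Protocol 4.1.4), so 50 × 2% = about 100% after a prophylactic dose.
- At least 12 patients with both profiles, 15 planned (Protocol 4.1).

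**Formula.** Assume linear one-compartment kinetics, and let q = 2^(−96/t½) be the fraction left after one interval. With equal doses the true ratio is R = 1/(1 − q). If the visit 7 dose is d times the visit 2a dose, and earlier doses were nominal at 96 h intervals, the carry-over into visit 7 is q/(1 − q). The planned ratio is then d + q/(1 − q). A dose difference of q/(1 − q) therefore equals the whole accumulation.

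| t½ assumed (h) | q | True R | Dose difference equal to the accumulation |
|---|---|---|---|
| 12 | 0.0039 | 1.004 | 0.4% |
| 16 | 0.0156 | 1.016 | 1.6% |
| 18 | 0.0248 | 1.025 | 2.5% |
| 19 | 0.0301 | 1.031 | 3.1% |
| 24 | 0.0625 | 1.067 | 6.7% |

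**Cross-check on the range.** Protocol 2.2 expects levels in the moderate range on this regimen. Taking a single-dose level at 96 h of 1% to 5% after a peak of 100% (the 5% limit is an assumption), R runs from 1/(1 − 0.01) = 1.010 to 1/(1 − 0.05) = 1.053, with implied half-lives of 14.4 to 22.2 h.

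**Effect of a dose difference.** The dose-adjusted ratio is [d + q/(1 − q)]/d.

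| t½ (h) | Visit 7 dose vs visit 2a | Planned ratio | Dose-adjusted ratio | True R |
|---|---|---|---|---|
| 16 | −3% | 0.986 | 1.016 | 1.016 |
| 18 | −5% | 0.975 | 1.027 | 1.025 |
| 18 | +5% | 1.075 | 1.024 | 1.025 |
| 19 | −3% | 1.001 | 1.032 | 1.031 |
| 19 | +3% | 1.061 | 1.030 | 1.031 |
| 24 | −5% | 1.017 | 1.070 | 1.067 |

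A numerical check, with linear trapezoids at 0.5, 1, 4, 12, 24, 48, 72 and 96 h and log-linear back-extrapolation to time 0, gave the same values. For dose differences up to 5% and half-lives up to 24 h, the adjusted ratio stays within 0.004 of the true one.

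**Group mean.** If the dose ratio varies at random with an assumed SD of 2%, 3% or 5%, the 95% half-width from dose alone at n = 12 is 1.96 × SD/√12 = 1.1, 1.7 or 2.8 percentage points.

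**What a few per cent means in practice.** A vial is 2000 IU in 4.3 mL (Protocol 6.1), or 465 IU/mL, so 0.1 mL is 46.5 IU. At an assumed 60 kg the dose is 3000 IU and 0.1 mL is 1.6% of it. If the IU dose were held fixed, a 3% weight gain would change IU/kg by 1/1.03 − 1 = −2.9%.

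**The case against.** The best defence is that dose is already controlled by design. Both sessions are 50 IU/kg by weight, the flowchart schedules weight repeatedly, and doses given at the site are supervised. A reader might infer from the 28-week gap and the inclusion of adolescents that the visit 7 dose will be systematically off. The documents do not support that: growth alters IU/kg only if the dose is not recalculated, and nothing says it will not be. Nor do they name any cause of a shift common to all patients. Random differences partly average out. This stands, and it makes the point conditional.

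A second defence is that dose-based comparisons of the sessions already exist in clearance and incremental recovery, both listed endpoints. That is true, and it limits the harm. But clearance uses AUC(0-inf) at single dose and AUC(0-96h) at steady state, so under linear kinetics it checks whether elimination is unchanged over time. It does not estimate accumulation.

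Third, dividing by the recorded dose cannot correct a draw-up error that nobody recorded, and carry-over at visit 7 comes from earlier doses, so the adjustment is not exact. Both limits stand; the second is small, as shown above.

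A reader might also infer that AUC, C30min and C96h should be rescaled to 50 IU/kg. That goes too far. C30min and C96h are defined as recorded activity, so rescaling changes what those listed endpoints measure. Linear scaling is also inexact, because there is no wash-out before visit 7 and pre-dose activity up to 5% is retained at visit 2a. Incremental recovery already gives a dose-normalised, baseline-subtracted measure at 30 minutes.

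Finally, exceptional outlier profiles may be excluded before database lock. This could catch a gross dosing deviation, but not one of a few per cent.

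**Conclusion.** The point holds as a minor, conditional one. The ratio omits the dose in both documents, and the expected accumulation is small enough (0.4% to 6.7% for assumed half-lives of 12 to 24 h) that a recorded dose difference of a few per cent could match or hide it. A 3% difference exceeds the accumulation for half-lives up to about 18.8 h, and a 5% difference up to about 22 h; above that the difference must be larger. If the recorded IU/kg are equal, the plain ratio is the usual one and nothing changes.

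The conclusion rests on linear one-compartment kinetics, nominal earlier doses at 96 h intervals, an assumed half-life, and dose differences whose size the documents do not give. The effect is strongest for individual ratios and weaker for the mean. No hypothesis is tested on the ratio, and it is not a listed secondary endpoint.

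**What to change.** In Protocol Table 9-1 and SAP Table 2, define the accumulation ratio as (AUC(0-96h) / actual IU/kg injected) at visit 7 divided by (AUC(0-96h) / actual IU/kg injected) at visit 2a, using the recorded dose and the body weight at that visit. Keep the unadjusted ratio in the listings. State that the adjustment is approximate because carry-over at visit 7 comes from earlier doses, and that it does not address unrecorded draw-up error. Leave the main analyses of AUC, C30min and C96h unscaled.

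The cost is one line in each table and one programming step. Protocol section 6.4 already requires all doses in the eCRF, and the dose is needed for clearance and incremental recovery in any case. No new data are required, and nothing about dosing changes. Fixing the rule before database lock also avoids a post-hoc choice between the two versions if the recorded doses prove unequal.
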